5.6.2 Dose Limiting Toxicity

Each subject in a dose level in Phase 1b is monitored every week by Eisai clinical team and the principal investigators or more frequently if necessary. DLTs are declared by both parties as well as the decisions to expand/continue or decrease the dose level cohort. The dose limiting toxicities will be presented.

5.6.3 Deaths, Serious and Other Significant Adverse Events

The adverse event verbatim descriptions (investigator terms from the eCRF) will be classified into standardized medical terminology using the Medical Dictionary for Regulatory Activities

(MedDRA) version 19.0 or later. Adverse events will be coded to primary System Organ Class (SOC) and preferred term (PT) using MedDRA.

A treatment-emergent adverse event (TEAE) is defined as an adverse event that had an onset date, or a worsening in severity from baseline (pre-treatment), on or after the first dose of study drug up to the last visit, or 30 days following the last dose of study drug. In addition, if an AE reemerges during treatment, having been present at pretreatment (Baseline) but stopped before treatment, it is also counted as a TEAE. Due to the use of pembrolizumab, serious adverse events (SAEs) occurring up to 90 days after the last dose of study drug will be considered as treatment-emergent serious adverse events.

Only those AEs that are treatment emergent will be included in summary tables. All AEs, treatment emergent or otherwise, will be presented in subject data listings. Treatment-emergent AEs (TEAEs) will be summarized.

The incidence of TEAEs will be reported as the number (percent) of subjects with TEAEs within SOC and PT. Subjects will be counted only once within a SOC and PT. If the subject experienced more than one TEAE within a specific SOC and PT, the subject will be counted with the worst grade for that AE. The number (percent) of subjects with TEAEs will also be summarized by highest Common Terminology Criteria for Adverse Events (CTCAE) grade. In summary, the following TEAE tables will be provided:

- Overview of TEAEs.
- TEAEs by SOC, PT, and CTCAE grade.
- TEAEs with CTCAE grade ≥ 3
- TEAE with outcome of death.
- Treatment-related TEAEs by SOC, PT, and CTCAE grade
- Treatment-related TEAEs with CTCAE grade ≥ 3
- Treatment-related TEAEs with outcome of death

The following subject AE listings (regardless treatment emergent or not) will be provided:

- All adverse events.

A subject data listing of all deaths will be provided with the information of primary reasons of deaths, deaths within 30 days of last dose, deaths > 30 days of last dose, and treatment-related deaths.

The number (percent) of subjects with treatment-emergent serious adverse events will be summarized by MedDRA SOC and PT. A subject data listing of all SAEs will be provided. The number (percent) of subjects with TEAEs leading to discontinuation, dose reduction, or dose interruption from study treatment will be summarized by MedDRA SOC and PT. A subject data listing of all AEs leading to discontinuation, dose modification, or dose interruption from study treatment will be provided. In summary, the following TEAE tables will be provided:

- SAEs
- Treatment related SAEs
- TEAEs leading to study drug dose interruption by SOC and PT.
- TEAEs leading to study drug dose reduction by SOC and PT.
- TEAEs leading to study drug discontinuation by SOC and PT.
- Clinically significant TEAEs (CSAE) for lenvatinib, by PT and CTCAE grade (any grade vs ≥ 3).
- TEAEs of special interest (AEOSI) for pembrolizumab, by PT and CTCAE grade (any grade vs ≥ 3).

The following subject AE listings (treatment emergent or not) will be provided:

- All deaths for all enrolled subjects.
- All serious adverse events (SAEs).
- All fatal TEAE
- All AEs leading to dose interruption
- All AEs leading to dose reduction.
- All AEs leading to study drug discontinuation.

5.6.4 Laboratory Values

Laboratory values that are non-missing and reported as ‘below the detectable limit’ of an assay will be replaced by half the detectable limit in the summary tables. Laboratory results will be summarized using the *Système international* (SI) units. Laboratory test results will be assigned a low/normal/high (LNH) classification according to whether the value was below (L), within (N), or above (H) the laboratory parameter’s reference range. Abnormal laboratory values will be identified as those outside the normal range. The abnormal values will be indicated in data listings. Laboratory parameters will also be categorized according to CTCAE v4.03 grades, and shifts from baseline CTCAE grades to worst grades will be assessed.

For quantitative parameters, the actual value and the change from baseline to each post-baseline visit, will be summarized by visit using descriptive statistics if needed. Urinalysis parameters (qualitative) will be listed.

Only laboratory parameters specified in the protocol will be summarized. Other laboratory parameters collected for some individual subjects will be presented in listings.

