The effect of lenvatinib-pembrolizumab combination therapy on soluble, tissue, genetic and/or imaging biomarkers will be summarized using descriptive statistics using the pharmacodynamic analysis set.

Safety Analyses:

Safety analyses will be performed on the Safety Set. Safety data will be summarized using descriptive statistics. Categorical variables will be summarized by number and percentage. Continuous variables will be summarized using n (number of subjects with available data), mean, standard deviation (SD), median, and range (minimum and maximum) unless otherwise specified. Laboratory test results will be summarized using 3 categories, hematology, liver and renal, and other clinical chemistry. Hematology and clinical chemistry parameters that are graded by CTCAE v 4.03 will be summarized by CTCAE grade. Shifts from baseline to the worst CTCAE grade will be tabulated.

Selected safety analyses may be performed if needed for subjects with the combination of lenvatinib and pembrolizumab as the first line treatment versus other subjects with prior systemic therapies. For the renal cell carcinoma cohort, safety subgroup analyses may be presented for treatment naïve subjects, subjects who were previously treated with an anti-PD-1/PD-L1 therapy, and subjects who were previously treated without an anti-PD-1/PD-L1 therapy.

Sample Size Rationale

Phase 1b: A sample size of 10 to 30 subjects will be enrolled to assess MTD. This is not based on statistical power considerations.

Phase 2: A sample size of 10 evaluable subjects will be enrolled per cohort, with the possibility of expansion to 20 evaluable subjects per cohort, depending on the evaluation by the sponsor and investigators of the efficacy and safety results observed with the initial 10 evaluable subjects in each cohort.

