9.5.1.5.1 ADVERSE EVENTS AND EVENTS ASSOCIATED WITH SPECIAL SITUATIONS

An AE is any untoward medical occurrence in a patient or clinical investigation subject administered an investigational product. An AE does not necessarily have a causal relationship with the medicinal product. For this study, the investigational products are lenvatinib and pembrolizumab.

The criteria for identifying AEs in this study are:

- Any unfavorable and unintended sign (including an abnormal laboratory finding), symptom, or disease temporally associated with the use of an investigational product, whether or not considered related to the investigational product (Note: Every sign or symptom should not be listed as a separate AE if the applicable disease [diagnosis] is being reported as an AE.)
- Any new disease or exacerbation of an existing disease. However, worsening of the primary disease should be captured under efficacy assessments as disease progression rather than as an AE.
- Any deterioration in nonprotocol-required measurements of a laboratory value or other clinical test (eg, ECG or x-ray) that results in symptoms, a change in treatment, or discontinuation of study drug
- Recurrence of an intermittent medical condition (eg, headache) not present pretreatment (Baseline)
- An abnormal laboratory test result should be considered an AE if the identified laboratory abnormality leads to any type of intervention, withdrawal of study drug, or withholding of study drug, whether prescribed in the protocol or not.

All AEs observed during the study will be reported on the CRF. All AEs, regardless of relationship to study drug or procedure, should be collected beginning from the time the subject signs the study ICF and for 30 days after the last dose of study treatment. Subjects who fail screening primarily due to AE(s) must have the AE(s) leading to screen failure reported. SAEs will be collected for 90 days after the last dose or 30 days following the last dose if the subject initiates new anticancer therapy, whichever is earlier. An AE will not be reported on the Adverse Event CRF if other anticancer treatment is started. All SAEs will be reported on the Adverse Event CRF. All deaths will be collected for 30 days following the last dose of study treatment and reported on the Survival CRF.

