9.5.1.5.3 LABORATORY MEASUREMENTS

Clinical laboratory tests to be performed, including hematology, chemistry, and urinalysis, are summarized in Table 7. Subjects should be in a seated or supine position during blood collection. The Schedule of Procedures/Assessments (Table 8 and Table 9) shows the visits and time points at which blood for clinical laboratory tests and urine for urinalysis will be collected in the study.

Table 7 Clinical Laboratory Tests

Category	Parameters
Hematology	Hematocrit, hemoglobin, platelets, RBC count, and WBC count with differential INR ^b
Clinical Chemistry	
Electrolytes	Bicarbonate, calcium, chloride, magnesium, phosphorus, potassium, sodium
Liver function tests	Alanine aminotransferase, alkaline phosphatase, aspartate aminotransferase, direct bilirubin, total bilirubin
Renal function tests	Blood urea nitrogen, creatinine
Thyroid function tests ^a	TSH and free T4 levels
Other	Albumin, cholesterol, glucose, lactate dehydrogenase, total protein, triglycerides, amylase, lipase
Urinalysis	Glucose, ketones, pH, protein, RBCs, specific gravity

RBC = red blood cell, T4 = thyroxine, WBC = white blood cell, INR, International Normalized Ratio.

a. Thyroid function will be assessed every 2 cycles.

b. Only at screening/baseline and when clinically indicated.

All hematology, blood chemistry (including pregnancy test, as applicable), and urinalysis samples are to be obtained prior to study drug administration and results reviewed prior to administration/dispensing of study drug at the beginning of each treatment cycle.

A laboratory abnormality may meet the criteria to qualify as an AE as described in this protocol (see [Section 9.5.1.5.1](#) and the CRF Completion Guidelines (CCG)). In these instances, the AE corresponding to the laboratory abnormality will be recorded on the Adverse Event CRF.

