9.7.1.8.3 LABORATORY VALUES

Laboratory results will be summarized using Système International units, as appropriate. For all quantitative parameters listed in [Section 9.5.1.5.3](#), the actual value and the change from baseline to each postbaseline visit and to the end of treatment will be summarized by visit and treatment using descriptive statistics. Qualitative parameters listed in [Section 9.5.1.5.3](#)

will be summarized using frequencies (number and percentage of subjects), and changes from baseline to each postbaseline visit and to the end of treatment will be reported using shift tables. Percentages will be based on the number of subjects with both nonmissing baseline and relevant postbaseline results.

Laboratory parameters will be categorized according to CTCAE v4.03 grades, and shifts from baseline CTCAE grades to maximum and final postbaseline grades will be assessed. CTCAE v4.03 will be used to identify subjects with treatment-emergent markedly abnormal laboratory values (TEMAV). A more detailed definition of TEMAV will be specified in the SAP. A summary of TEMAVs will be presented by visit and overall and by treatment group.

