5.6.6 Electrocardiograms

Electrocardiogram (ECG) assessments will be performed at screening and at Day 1 of each cycle. Descriptive statistics for electrocardiogram parameters (HR, PR, QRS, QT, QTcB, QTcF and RR) and changes from baseline will be presented by visit. ECG findings (categorized as normal; abnormal, not clinically significant; and abnormal, clinically significant) will be summarized using shift tables. A subject data listing will also be provided.

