7 CHANGES IN THE PLANNED ANALYSES

Not applicable.

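### SAP 5.6.4 makes urinalysis listing-only, although protocol 9.7.1.8.3 plans n (%) and shift tables that cover dipstick protein, and SAP 7 records no change

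*SAP*

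**What the plan says.** Protocol 9.7.1.8.3 says of the qualitative parameters in Section 9.5.1.5.3 that they "will be summarized using frequencies (number and percentage of subjects), and changes from baseline to each postbaseline visit and to the end of treatment"; the sentence ends by putting those changes in shift tables. It also fixes the denominator: "Percentages will be based on the number of subjects with both nonmissing baseline and relevant postbaseline results". The urinalysis row of Table 7 in 9.5.1.5.3 reads "Glucose, ketones, pH, protein, RBCs, specific gravity".

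SAP 5.6.4 says: "Urinalysis parameters (qualitative) will be listed". SAP 7, on changes to the planned analyses, says: "Not applicable".

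The protocol synopsis is narrower than the protocol body: "Laboratory test results will be summarized using 3 categories, hematology, liver and renal, and other clinical chemistry". Urinalysis is not among the three categories, but the synopsis does not say that it will only be listed.

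**The concern.** A listing is not a summary. A reader of the study report who wants to know how many subjects moved from negative or trace protein at baseline to 2+ or more would have to count line by line. Proteinuria is a lenvatinib toxicity with its own management section (protocol 9.4.1.1.3), and the dipstick is scheduled throughout treatment, so the data are collected systematically. The protocol promised a table of them. The SAP withdraws it, and the section meant for such departures does not say so.

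At stake is one descriptive safety output: an incidence and shift summary of dipstick protein that does not pass through the investigator's decision to report an adverse event.

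**Working it through.** The plan gives no figure to reproduce here. The check sets the texts side by side, with a few counts.

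1. **Scope.** Table 7 names 6 urinalysis parameters: glucose, ketones, pH, protein, RBCs and specific gravity. Protocol 9.7.1.8.3 refers to that section by number, and the SAP itself labels urinalysis as qualitative. Protein, 1 of the 6, is therefore within the protocol's rule.

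2. **Planned summaries of dipstick protein.** Protocol: n (%) (1) + shift to each post-baseline visit (1) + shift to end of treatment (1) = 3. SAP 5.6.4: 0.

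3. **Other SAP text that might restore them.**
   - SAP 5.6.4 has a general sentence on shifts from baseline to worst CTCAE grade. It does not name urinalysis, and the grading table in Appendix 13.6 is titled for hematology and clinical chemistry.
   - SAP 5.6.4 also says that protocol-specified laboratory parameters are summarised and others are listed. Urinalysis is protocol-specified, yet is treated like the others.
   - No other SAP section seen plans a urinalysis table.

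4. **Version gap.** The SAP follows Amendment 8 and the protocol is at Amendment 9. The change-log rows seen for those two amendments do not mention 9.7.1.8.3, so the gap does not appear to explain the difference.

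5. **What the TEAE tables capture.** Protocol 9.5.1.5.1 states: "An abnormal laboratory test result should be considered an AE if the identified laboratory abnormality leads to any type of intervention"; withholding study drug also qualifies. Proteinuria that interrupts or reduces lenvatinib should therefore appear in the TEAE tables of SAP 5.6.3. Under protocol Table 2, however, Grade 1 and tolerable Grade 2 toxicity means continued treatment at the same dose. Such a result need not meet that rule, and 9.5.1.5.1 leaves isolated laboratory abnormalities to the investigator's judgement.

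6. **Number of subjects affected.** The documents give neither a proteinuria rate nor the share of positive dipsticks reported as adverse events. The number whose proteinuria would appear only in listings runs from 0 (every positive dipstick reported) up to all subjects whose positive dipsticks led to no action.

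7. **Other trimmed laboratory output.** Protocol 9.7.1.8.3 plans shifts to both maximum and final CTCAE grade; SAP 5.6.4 keeps only the worst. The protocol also plans a summary of treatment-emergent markedly abnormal values (TEMAVs), to be defined in the SAP; SAP 5.6.4 does not mention it. By-visit summaries of quantitative parameters become conditional on need.

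8. **Output needed for the full protocol version.** Table 9 schedules urinalysis on Cycle 1 Day 15 (1 visit) and on Day 1 of Cycles 2 to 8 (7 visits). That gives 1 + 7 = 8 post-baseline visits in the Phase 2 Treatment Phase alone, before conditional Day 15 visits, the Extension Phase and the Off-Treatment visit. For one parameter this is at least 8 shift panels per cohort, or 8 × 6 = 48 over six cohorts. A table with two panels (worst post-baseline, end of treatment) needs 2 × 6 = 12 panels, in six tables.

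**The case against.** The strongest case on the other side has four parts.

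- **The dipstick is a screening test.** Protocol 9.4.1.1.3 grades proteinuria on the 24-hour urine result. That collection is required at the first dipstick of 2+ or more, at a later increase on the same lenvatinib dose level, and at 2+ or more after a dose reduction. Graded events reported as adverse events appear by preferred term and grade, and in the interruption, reduction and discontinuation tables. SAP 5.6.3 also plans a table of clinically significant TEAEs for lenvatinib, although its terms are not listed, so whether proteinuria is among them is unknown. This stands, and it limits the impact.
- **The protocol is not uniform.** The synopsis names no urinalysis category, and 9.7.1 leaves further detail to the SAP. This has some weight, but 9.7.1.8.3 is explicit, and removing a planned output is more than a detail.
- **Part of the record was not seen.** The table shells are in a separate document (SAP 11), and the SAP's summary of changes from version 3 to 4 was not available to me. The statement that no change is recorded therefore applies to SAP 7 only.
- **Nothing comparative depends on it.** The study is single-arm, so no contrast between arms uses this table. This also stands.

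Three stronger readings are tempting and not supported. A reader might infer that proteinuria drops out of safety reporting; it does not, for the reasons above. A reader might infer that urinalysis alone was cut; step 7 shows otherwise. A reader might infer that the SAP has abandoned shift tables for qualitative safety data; it has not, since SAP 5.6.6 says that "ECG findings (categorized as normal; abnormal, not clinically significant; and abnormal, clinically significant) will be summarized using shift tables", though without the by-visit and end-of-treatment detail that protocol 9.7.1.8.5 gives for ECGs.

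**Conclusion.** The mismatch is real and its consequence is minor. The SAP text replaces the planned frequency and shift tables for urinalysis with a listing, and SAP 7 does not acknowledge it. For dipstick protein that is 3 planned summaries against 0. The loss is confined to a tabulation that would show low-grade or unreported proteinuria independently of adverse event reporting. Efficacy results, cohort expansion decisions and subject management are not affected, and the data remain available in listings.

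This rests on two assumptions: that the separate table shells follow the SAP text, and that investigators report actionable proteinuria as protocol 9.5.1.5.1 requires. If the shells already contain a dipstick table, only the wording of SAP 5.6.4 needs correcting.

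**What to change.** In SAP 5.6.4, add one table per cohort for dipstick protein. It should give n (%) by category, the shift from baseline to worst post-baseline value, and the shift from baseline to end of treatment. Base percentages on subjects with both a baseline and a relevant post-baseline result, as protocol 9.7.1.8.3 requires. The SAP 8 convention that shift tables use scheduled and unscheduled assessments suits the worst-value panel, because repeat dipsticks would then count.

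In SAP 7, replace the present entry with a short statement that the each-visit shifts and the other five urinalysis parameters (6 − 1 = 5) are listing-only, with the reason. The same entry is the natural place to record the omitted shift to final CTCAE grade and the omitted TEMAV summary, unless these are restored.

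The cost is one compact descriptive table per cohort from data already collected, plus a few sentences. The protocol's full by-visit version would take considerably more output, as step 8 of the working shows, and is not needed to recover the useful information.

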5.6.5 Vital Signs

Vital sign values will be evaluated on an individual basis by subject. Descriptive statistics for vital signs parameters (diastolic and systolic blood pressure, resting HR, respiratory rate, body temperature, and weight) and changes from baseline will be presented.

5.6.6 Electrocardiograms

Electrocardiogram (ECG) assessments will be performed at screening and at Day 1 of each cycle. Descriptive statistics for electrocardiogram parameters (HR, PR, QRS, QT, QTcB, QTcF and RR) and changes from baseline will be presented by visit. ECG findings (categorized as normal; abnormal, not clinically significant; and abnormal, clinically significant) will be summarized using shift tables. A subject data listing will also be provided.

5.6.7 Other Safety Analyses

Left ventricular ejection fraction (LVEF) obtained on echocardiogram or MUGA scans will be summarized with descriptive statistics for baseline and post-baseline lowest value. Percent change of the post-baseline lowest value from baseline will be presented. A subject data listing

will be provided.

5.7 Exploratory Analyses

The exploratory analyses as described in [Section 5.5](#) (Pharmacokinetic, Pharmacodynamic, Pharmacogenomic and Other Biomarker Analyses) will be reported separately from the clinical study report.

6 INTERIM ANALYSES

The evaluation of efficacy and safety by the sponsor and investigators will occur on the initial 10 evaluable subjects while enrollment is ongoing. Based on the outcome of the evaluation the enrollment could be suspended before enrolling the planned 20 subjects in each cohort.

The endometrial carcinoma cohort may be expanded to approximately 120 evaluable subjects. Two interim analyses will take place when 21 and 60 subjects have sufficient follow-up to be evaluated for response. The decision to expand enrollment will be based on the results of the 2 interim analyses, which will spend $\beta = 0.012$ and $\beta = 0.024$ at the first and second interim analyses, respectively. Based on an assumption of H_0 : 16% ORR and H_1 : 34% ORR, at 2-sided $\alpha = 0.02$, this design will give 97% statistical power with 120 subjects. At the first interim analysis ($N = 21$), if there are more than 3 responses, then approximately 40 additional subjects will be enrolled. At the second interim analysis ($N = 60$), if there are more than 12 responses, approximately 60 additional subjects will be enrolled. If there are 12 or fewer responses, the sponsor may decide whether to expand enrollment based on clinical outcome, eg, ORR and DOR. If the expansion beyond 60 subjects does not happen, this design for the endometrial carcinoma cohort has approximately 86% power at 2-sided $\alpha = 0.02$.

The renal cell carcinoma cohort may be further expanded to approximately 120 evaluable subjects. The decision to expand enrollment will be based on the results of 2 interim analyses.

The first interim analysis will take place when 22 subjects (11 treatment naïve and 11 previously treated without an anti-PD-1/PD-L1 therapy) have sufficient follow-up to be evaluated for response. At the first interim analysis ($N = 22$), if there are more than 5 responses, then approximately 45 additional subjects will be enrolled. It is anticipated that the additional

45 subjects will consist of approximately 12 treatment naïve subjects enrolled under Amendment 05 and approximately 33 previously treated subjects who have received 1 or 2 prior therapies and have progressed on treatment with an anti-PD-1/PD-L1 mAb. The second interim analysis will include these 45 additional subjects and the 11 treatment naïve subjects included in the first interim analysis and will take place when these 56 subjects have sufficient follow-up to be evaluated for response. At the second interim analysis, whether the previously treated renal cell carcinoma subset will be further expanded will be decided based on clinical review of both efficacy and safety data.

